### 1.2. Secondary Objectives

1.2.1. To examine the impact of an eHealth intervention for insomnia on the clinical severity of insomnia symptoms in adult survivors of childhood cancer.

Hypothesis 1.2.1.: A larger proportion of survivors randomized to the CBTi intervention will no longer meet clinical criteria for insomnia post-intervention compared to survivors randomized to online patient education.

1.2.2. To determine whether treatment of insomnia symptoms will improve neurocognitive function in adult survivors of childhood cancer with both insomnia and neurocognitive impairment.

Hypothesis 1.2.2.a.: Survivors randomized to an eHealth CBTi intervention will report significantly fewer symptoms of neurocognitive impairment post-intervention compared to survivors randomized to online patient education only.

Hypothesis 1.2.2.b.: Improvement in insomnia symptoms will mediate the association between intervention status (CBTi vs. online patient education) and improved neurocognitive function post-intervention.

Hypothesis 1.2.2.c.: Symptoms of emotional distress and cardiac health will be associated with improved insomnia symptoms and neurocognitive function.

1.2.3. To explore the mediating effects of improved neurocognitive function, emotional distress, and cardiovascular health on the association between insomnia symptoms and quality of life.

Hypothesis 1.2.3.a.: Survivors with improved insomnia symptoms following completion of an eHealth CBTi intervention will report better health-related quality of life compared to survivors without improved insomnia symptoms.

Hypothesis 1.2.3.b.: Neurocognitive function, symptoms of emotional distress, and biomarkers of cardiovascular health following completion of the eHealth CBTi intervention will mediate the association between improved insomnia symptoms and quality of life 6-months post-intervention.

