#### **4.3. Study Procedures:**

##### **Assessment of Sleep**

1) Insomnia Severity Index (ISI) is a 7-item, Likert scale, self-report questionnaire assessing perception of sleep and consequences of insomnia. The ISI has had extensive validity and reliability testing, including for electronic delivery and for use in evaluating treatment response. Cronbach  $\alpha$  for internal consistency is 0.90, convergent validity with measures of fatigue, quality of life, anxiety and depression have been reported. The scores range from 0 (no insomnia) to 28 (severe insomnia); scores  $< 7$  are considered “no clinically significant insomnia”. The ISI will be administered at baseline, post-intervention, and 6-month follow-up.

2) Sleep Diary will be an online diary and will be included in the SHUTi program (including the patient education arm). Each diary entry contains 10 standard sleep questions including bedtime, sleep onset latency, number of awakenings, total length of awakenings, wake time, arising time, daytime naps, rating of soundness of previous night's sleep, rating of refreshed feeling upon morning awakening and inquiry about sleep aids (over the counter medication/alcohol). In addition to the 10 pre-assessment entries required before the intervention begins, participants are encouraged to complete the diary daily, but entries that are up to 3 days old will be accepted. Sleep diary data will generate data on sleep onset latency (SOL), wake after sleep onset (WASO), sleep efficiency (SE) and number of awakenings. Data from the sleep diaries will be correlated with actigraphy data.

3) Actigraphy will be collected to measure sleep-patterns of each participant. A WHOOP wrist monitor to be worn over 7 to 11 consecutive days at three specified intervals [baseline, post-intervention, 6 months]. Actigraphy provides objective assessment of wrist movement that infers wakefulness and sleep.

St. Jude Children's Research Hospital

IRB NUMBER: 19-0121

IRB APPROVAL DATE: 05/04/2021

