## Emotional Distress

Symptoms of emotional distress will be assessed using the Patient Health Questionnaire – 9 (PHQ-9) for depression and the Generalized Anxiety Disorder – 7 (GAD-7). The PHQ-9 is designed for the screening and monitoring of depressive symptoms as well as for the presence and duration of suicide ideation. The PHQ-9 provides cut-off scores for mild, moderate, moderately severe, and severe depression. PHQ-9 scores >10 have sensitivity of 88% and specificity of 88% for major depression. The GAD-7 is designed for the screening and monitoring of anxiety symptoms. Cut-off scores are provided for mild, moderate, and severe anxiety. Using the threshold score of 10, the GAD-7 has a sensitivity of 89% and a specificity of 82% for generalized anxiety disorder. These questionnaires have undergone reliability and validity testing across individuals with range of health conditions and demographic characteristics. The PHQ-9 and GAD-7 will be administered at baseline, post-intervention, and 6-month follow-up via the RICE Platform.

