direct relationships between change in ISI (baseline to post-intervention) with emotional distress and cardiac health indices at postintervention time points and with HRQoL measures. To establish whether a mediation relationship exists, we will follow standard methodology by 1) establishing that there is an association between the causal variable (e.g. CBTi intervention) and the outcome (e.g. neurocognitive impairment), 2) establishing the association between the causal variable and the mediator and 3) showing that the mediator is associated with the outcome variable in a model with the causal variable included and 4) in the same model as used to evaluate step 3, determine that the relationship between the causal variable and the outcome variable is attenuated by inclusion of the mediator in the model. We do not expect to observe complete mediation in any of our investigations. Specifically, the above methodology will be used to test hypothesis 1.2.2.b with the causal variable defined as CBTi intervention, mediator as change in insomnia (ISI) and outcomes as neurocognitive indices. Hypothesis 1.2.2.c will consider change in insomnia as the causal variable, neurocognitive function indices, emotional distress symptoms and cardiovascular risk indices as mediators for the outcome HRQoL at 6 months. In addition to the stepwise model-based approach outlined above, we will also evaluate relationships using Structural Equation Modelling (SEM) approaches to evaluating mediation, which would allow simultaneous evaluation of the multiple pathways and classes of variables together in a single model, with improved power, allowing estimates of direct and indirect effects calculated from each. All effects size estimates (mean differences and/or odds ratios) will be presented along with associated confidence intervals and two-sided p-values, both unadjusted and adjusted for multiple comparisons. Primary therapies for childhood cancer have been associated with insomnia and study outcomes (neurocognitive morbidities, emotional distress, cardiovascular risk). Because our study inclusion criteria require that survivors have observed neurocognitive deficits we do not expect differential responses to SHUTi by previous childhood cancer treatment exposures. However, chemotherapy exposures and radiation doses are abstracted from medical records and cumulative doses of methotrexate (high dose and intrathecal), cytarabine, and cranial radiation will be included as covariates in relevant analyses. In addition, we will conduct sensitivity analyses to examine their contributions to treatment response.

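### Section 9.1 relates change in ISI to PHQ-9 distress without any analysis that separates sleep content from mood; if the study's PHQ-9 form has a sleep item, the association is biased away from zero

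*Combined protocol and SAP*

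**What the plan says.** **Measures.** Section 4.3 (Emotional Distress) states that "Symptoms of emotional distress will be assessed using the Patient Health Questionnaire" and, for anxiety, the GAD-7. It describes their content only in general terms: "The PHQ-9 is designed for the screening and monitoring of depressive symptoms as well as for the presence and duration of suicide ideation", and "The GAD-7 is designed for the screening and monitoring of anxiety symptoms". It lists no items. Section 4.3 (Assessment of Sleep) describes the ISI as a "self-report questionnaire assessing perception of sleep and consequences of insomnia" and notes reported convergent validity with fatigue, anxiety and depression measures, without coefficients.

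**Hypotheses.** Hypothesis 1.2.2.c reads "Symptoms of emotional distress and cardiac health will be associated with improved insomnia symptoms and neurocognitive function". Hypothesis 1.2.3.b says "Neurocognitive function, symptoms of emotional distress, and biomarkers of cardiovascular health following completion of the eHealth CBTi intervention will mediate" the link between improved insomnia and later quality of life.

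**Analysis.** Section 9.1 examines "direct relationships between change in ISI (baseline to post-intervention) with emotional distress and cardiac health indices at postintervention time points". It then takes change in insomnia as the causal variable, with neurocognitive indices, "emotional distress symptoms and cardiovascular risk indices as mediators for the outcome HRQoL at 6 months". That mediation model is labelled 1.2.2.c in section 9.1, whereas section 1.2 states it as 1.2.3.b.

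**What is not there.** Neither section 4.3 nor 9.1 says whether the PHQ-9 enters these models as a total, a category or part of a latent construct. The planned sensitivity analyses concern adherence, cancer-treatment exposures and missing data. None addresses content shared by the sleep and distress scales.

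**The concern.** An association between two questionnaires says something about two constructs only if the questionnaires do not score the same symptom. Here the explanatory variable is change in an insomnia score, and one of the two distress measures is a depression score that may itself count disturbed sleep. If so, a participant who sleeps better and feels no different in mood would tend to improve on both scales.

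What is at stake is interpretation. The theoretical model in section 2.2 proposes that improving insomnia improves distress and, through it, quality of life. Shared content could produce the first of those links without any change in mood, and the plan as written gives no way to tell the two explanations apart on the PHQ-9. The false discovery rate adjustment in the plan addresses the number of tests and does not remove a bias of this kind.

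**Working it through.** **1. The plan's own figures.** The only power figures are for arm comparisons. With (1.960 + 0.842) × √(2/n per arm):
- 80 per arm: 0.443 (plan: 0.45)
- 70 per arm: 0.474 (plan: 0.48)
- 160 per arm: 0.313 (plan: 0.31)

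These reproduce. The plan gives no figure for the ISI-distress association, so there is nothing of its own to check there.

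**2. Inputs.** From the documents: 160 evaluable per sex and 320 combined at the post-intervention assessment, with all analyses first reported separately by sex. Everything else is assumed, because the documents give no PHQ-9 items, SDs or correlations:
- the PHQ-9 total contains one sleep item
- SD of that item: 0.8 to 1.0
- SD of the PHQ-9 total: 4 to 5.5
- correlation of the item with change in ISI: 0.25 to 0.7
- the other items are unrelated to change in ISI (no change in mood)

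The correlation range is wide for a reason. As the sentence survives, it relates *change* in ISI to distress *at* a time point, which reads as a level. A level would usually correlate less with a change score than with a score taken at the same time. If so, 0.25 to 0.55 is the more plausible part of the range.

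**3. Correlation produced by the item alone.** Signs are ignored.

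r = (item correlation) × (item SD) / (total SD)
- low: 0.25 × 0.8 / 5.5 = 0.036
- middle: 0.475 × 0.9 / 4.75 = 0.090
- upper end of the weaker range: 0.55 × 1.0 / 4 = 0.138
- high: 0.7 × 1.0 / 4 = 0.175

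**4. Chance of a nominally significant result.** Fisher's z: let λ = atanh(r) × √(n − 3). The chance of two-sided p<0.05 is Φ(λ − 1.96) + Φ(−λ − 1.96). √157 = 12.53 and √317 = 17.80.

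| r | λ, n=160 | chance | λ, n=320 | chance |
|---|---|---|---|---|
| 0.036 | 0.46 | 7% | 0.65 | 10% |
| 0.090 | 1.13 | 20% | 1.61 | 36% |
| 0.138 | 1.73 | 41% | 2.46 | 69% |
| 0.175 | 2.22 | 60% | 3.15 | 88% |

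The nominal rate is 5%. These chances apply to unadjusted p-values; the plan also reports adjusted ones, for which they would be lower.

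**5. Mediation steps in section 9.1, one by one.**
- Step 1 (change in ISI with quality of life) does not involve the PHQ-9.
- Step 2 (change in ISI with distress) is the same association as above and carries the same bias.
- Step 3 requires distress to predict quality of life with change in ISI already in the model.
- Step 4 requires the ISI coefficient to shrink when distress is added.

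Item overlap between the two scales inflates step 2. It does not by itself satisfy steps 3 and 4.

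**The case against.** **The premise is not in the documents.** Section 4.3 mentions depressive symptoms and suicide ideation and no sleep item. This stands, so the point must be conditional. It can be settled by looking at the form the study administers.

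**The wording is incomplete.** The sentence on direct relationships has lost its opening in the text available for review, so detail on scoring or covariates may be missing. This also stands. A category cut from a total that contains the item would still carry the overlap.

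**There is a second distress measure.** A PHQ-9 signal can be compared with the GAD-7. This is true and useful, but section 9.1 does not say how the two are to be read together, and an anxiety scale is not a sleep-free measure of depression.

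**The work is associative and partly exploratory, and using the intact instrument is conventional.** This is fair. It is why the remedy is an added analysis, not a replacement.

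**Stronger readings that do not hold.**
- A reader might infer that any fall in insomnia lowers the PHQ-9 by construction. With an item correlation of 0.25 to 0.7 it is only a tendency.
- A reader might infer that overlap alone could establish distress as the mediator of the quality-of-life gain. Only the cause-to-mediator step is affected.
- A reader might infer that a SHUTi-versus-education difference in PHQ-9 would be inflated. Section 4.1 names distress as a general aim, but the arm comparisons spelled out in section 9.1 are for sleep and neurocognition, so no specified analysis is in question.

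**Conclusion.** The gap is real and the conclusion conditional. The plan relates change in ISI to PHQ-9 and GAD-7 distress, uses distress as a mediator, and has no analysis separating sleep content from mood. If the PHQ-9 form contains a sleep item, the association tested under Hypothesis 1.2.2.c and the cause-to-mediator step of the quality-of-life mediation are biased away from zero.

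On the assumed inputs the artefact is small in size (r about 0.04 to 0.18). It still lifts the chance of nominal significance with unchanged mood to about 7% to 60% within one sex, the lead analysis, and to 10% to 88% if the sexes are combined. With the weaker item correlations (0.25 to 0.55) the single-sex range is 7% to 41%. A false link is therefore possible, not assured. None of these ranges is an estimate from trial data, and genuine mood improvement may also occur.

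**What to change.** First check the PHQ-9 form for a sleep item and state in section 9.1 how the PHQ-9 enters the models. If the item is there, add to section 9.1:
- Every ISI-distress association and every mediation model that uses the PHQ-9 will be repeated with the PHQ-9 score omitting its sleep item.
- GAD-7 results will be reported separately from PHQ-9 results.
- Improvement in insomnia will be described as linked to depressive symptoms only if the association persists in the sleep-free score.
- The full PHQ-9 is kept for description and severity cut-offs.

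In the same edit, reconcile the label of the quality-of-life mediation (1.2.2.c in section 9.1, 1.2.3.b in section 1.2).

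The cost is a few lines of SAP text and one derived score from item responses already collected, with no change in sample size, visits or instruments. The small downside is that published PHQ-9 cut-offs do not apply to the reduced score.

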in a randomized controlled trial including 44 adults with primary insomnia who were randomly assigned to either the internet intervention or wait-list control group. Sleep diary data showed significant improvements for SHUTi users in sleep efficiency (SE), nighttime awakenings (number and time spent awake), and total sleep time; whereas the control group showed no significant changes. SHUTi participants also showed clinical improvement in insomnia severity, where 73% of SHUTi users fell in the “no insomnia” category after treatment; no control participants met this criterion. In addition, although SHUTi was not specifically designed to target comorbid symptoms, significant improvements were found in mood (e.g., depressive and anxious affect), physical symptoms

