#### SHUTi

SHUTi is a fully automated, interactive and tailored web-based program that incorporates the primary tenets of face-to-face CBT-I, including sleep restriction, stimulus control, cognitive restructuring, sleep hygiene, and relapse prevention. Intervention content is presented in six "Cores," metered out over time. Each Core

was developed to parallel traditional weekly sessions conducted when delivering CBT-I in a face-to-face format, following a similar general structure: 1) examination of Core objectives, 2) review and feedback on homework and sleep diary data from the previous week, 3) teaching of new intervention material, 4) summary of the main points of the Core, and 5) assignment of homework. The participant will have nine weeks to complete the six cores and at week 10 will be asked to complete post-intervention questionnaires/sleep diaries as well as to complete the post intervention remote evaluation. Data will be available on total number of participant logins, sleep diaries completed, and core modules completed. All participants will be able to access human support through UVA for technical difficulties with SHUTi. Intervention content is enhanced through

St. Jude Children's Research Hospital

IRB NUMBER: 19-0121

IRB APPROVAL DATE: 05/04/2021

a variety of interactive features, including personalized goal-setting, graphical feedback based on reported symptoms, animations and illustrations to enrich comprehension, quizzes to test and enhance user knowledge, vignettes to promote identification with material, and video-based expert explanations. Weekly automated emails are also sent to increase engagement and encourage program adherence. However, no human support will be provided to increase treatment adherence. Removing human support from provision of care can vastly increase the ability to widely disseminate treatment, however, it may be associated with reduced adherence. Despite this, a recent study of SHUTi with breast cancer survivors indicated that intervention group participants completed 4.1 (SD = 2.5) cores, with 82.1%, 75.1%, 67.2%, 64.2%, 62.7%, and 59.7% completing cores 1, 2, 3, 4, 5, and 6, respectively. The number of cores completed was associated with improvements in insomnia symptoms. Therefore, we will complete a sensitivity analysis to examine the impact of treatment adherence on insomnia symptoms.

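### The stepwise quality-of-life models take change in ISI as the cause and do not name randomised arm, so in a both-arm analysis part of any SHUTi effect by another route is credited to insomnia improvement

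*Combined protocol and SAP*

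**What the plan says.** Section 9.1 (Statistical Analysis) sets out a four-step mediation procedure and applies it twice.

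- **Neurocognition.** The plan will "test hypothesis 1.2.2.b with the causal variable defined as CBTi intervention, mediator as change in insomnia (ISI) and outcomes as neurocognitive indices". Arm is the causal variable here, so it is in the step 3 and step 4 models by construction.
- **Quality of life.** "Hypothesis 1.2.2.c will consider change in insomnia as the causal variable, neurocognitive function indices, emotional distress symptoms and cardiovascular risk indices as mediators", the outcome phrase being "as mediators for the outcome HRQoL at 6 months". The causal variable is now a post-randomisation change score.

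Step 3 requires "showing that the mediator is associated with the outcome variable in a model with the causal variable included". With ISI change as the cause, that step does not bring arm in. The covariates named are cancer-treatment exposures: "cumulative doses of methotrexate (high dose and intrathecal), cytarabine, and cranial radiation will be included as covariates in relevant analyses". Adjustment for the stratification factors is stated for the arm comparison of ISI change.

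An SEM is also planned, allowing "simultaneous evaluation of the multiple pathways and classes of variables together in a single model". Its nodes and paths are not listed. The text introducing the mediation analyses includes the CBTi intervention among the variables of interest.

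Section 9.1 labels the HRQoL model 1.2.2.c, but its content matches hypothesis 1.2.3.b in Section 1.2. Objective 1.2.3 is worded as exploratory.

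**The concern.** Objective 1.2.3 asks whether better sleep itself carries over to cognition, distress, cardiovascular indices and HRQoL. Randomised arm is expected to move ISI; that is the primary hypothesis. If arm also moves a mediator or HRQoL by some other route, it is a common cause of the supposed cause and the supposed effect. A both-arm regression without arm then shows an ISI slope even where ISI change does nothing.

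The plan makes another route plausible. Section 4.4 lists SHUTi's components, "including sleep restriction, stimulus control, cognitive restructuring, sleep hygiene, and relapse prevention", and cognitive restructuring could act on mood directly. Section 2.2 reports that in an earlier SHUTi trial "significant improvements were found in mood (e.g., depressive and anxious affect), physical symptoms", as well as QoL. Section 9.1 also says complete mediation is not expected in any of the investigations. Applied to 1.2.2.b, that means some arm effect on the neurocognitive indices outside ISI, and those indices are mediators in the HRQoL model.

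At stake is the mechanism claim. Adjusting for treatment doses does not remove confounding by arm, and the false discovery rate adjustment in the power section does not repair p-values that are biased under the null.

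**Working it through.** **Plan's own figures first.** The detectable effect at 80% power, two-sided 0.05, is (1.960 + 0.842) × √(2/n per arm):

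- n=80: 2.802 × 0.158 = 0.443 (plan 0.45)
- n=70: 2.802 × 0.169 = 0.474 (plan 0.48)
- n=160: 2.802 × 0.112 = 0.313 (plan 0.31)

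These reproduce. At 6 months, 70 per arm per sex gives 140 per sex and 280 in all. The plan gives no operating characteristics for the mediation models.

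**Model for the bias.** Allocation is 1:1, so the arm indicator A has variance 0.25. Within-arm SDs are 1, and both variables are signed so that higher means improvement. ISI change is X = dx·A + e. The mediator or HRQoL is Y = dy·A + u. The true X-to-Y slope is 0, and e and u are independent. Here dx = 0.31 and 0.45 are the plan's detectable effects; every other dx and every dy is an assumption.

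Without arm in the model:

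- slope = 0.25·dx·dy / (1 + 0.25·dx²)
- share of dy credited to ISI change = slope × dx / dy = 0.25·dx² / (1 + 0.25·dx²)

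| dx (SD) | share credited |
|---|---|
| 0.31 | 0.0240/1.0240 = 2.3% |
| 0.45 | 0.0506/1.0506 = 4.8% |
| 0.8 | 0.16/1.16 = 13.8% |
| 1.0 | 0.25/1.25 = 20% |

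**One cell by hand: dx=0.8, dy=0.3, n=280.** Slope = 0.06/1.16 = 0.052. Residual variance = 1 + 0.25 × 0.09 − 0.0517² × 1.16 = 1.019. SE = √(1.019/(280 × 1.16)) = 0.056. The ratio is 0.92, so the rejection probability is P(Z > 1.04) + P(Z < −2.88), about 15%.

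**Simulated rejection of a zero ISI slope** (8,000 data sets per cell):

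| dx, dy | slope without arm | n=280 | n=140 |
|---|---|---|---|
| 0.45, 0.3 | 0.03 | 8.6% | 5.8% |
| 0.45, 0.5 | 0.05 | 14.5% | 10.0% |
| 1.0, 0.3 | 0.06 | 19.8% | 12.6% |
| 1.0, 0.5 | 0.10 | 44.5% | 25.4% |

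With arm included, rejection is 4.4% to 5.2% in all of these. Over dx 0.5-1.0 and dy 0.2-0.5, the rates without arm run from about 7% to 45% at n=280 and 6% to 25% at n=140.

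**Joint rule.** Mediation under 1.2.3.b needs steps 1 to 3 to be met together. Simulated without arm, with direct arm effects on both mediator and HRQoL and no true ISI effect:

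- dx=0.8, dy=0.3, no mediator-to-HRQoL link: 0.1%
- dx=0.8, dy=0.3, link 0.5: about 7% (n=280), 3-4% (n=140)
- dx=0.8, dy=0.5, link 0.5: 24% (n=280), 10% (n=140)

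**What arm does not remove.** If a shared within-person factor gives ISI change and HRQoL a within-arm correlation of 0.2, the slope with arm included is 0.20, with rejection of about 92% at n=280 and 66% at n=140.

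**The case against.** Several stronger readings are tempting, and the documents do not support them.

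- *The whole of any other-route effect is credited to insomnia.* Only a share is, and a small one at the plan's detectable effects.
- *Arm is left out of every model.* This is fair for the stepwise models as written. For the SEM it is unspecified: the intervention is among the variables of interest, and the theoretical-model figure is not available. The sentence opening the ISI-change associations is also lost at a page break.
- *Both arms are certainly pooled.* Hypotheses 1.2.3.a and 1.2.3.b speak of improvement after completing CBTi. In a SHUTi-only analysis arm is constant and cannot confound. Section 9.1 states no such restriction, so the population is open.
- *The trial is unblinded, so reporting bias drives the result.* No masking is described, and the two websites differ visibly. An arm-related reporting shift is therefore possible, but it is an inference. It would not reach the measures that are not self-reported: CNS Vital Signs, blood markers and heart-rate variability.
- *The mediation claim has a false-positive rate above 5%.* That is shown for the single slope. The joint rule exceeds 5% only in some settings.

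It is also fair to say that the earlier SHUTi gains in mood and QoL may themselves have run through insomnia. The protocol notes that the programme was not designed to target comorbid symptoms, so the size of any direct effect is assumed. Adding arm cures only confounding by arm, and within-arm confounding may be larger. That limits what adjustment achieves but is no reason to omit it. The exploratory label lowers the stakes; the plan still promises p-values and direct and indirect effects for a stated hypothesis.

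**Conclusion.** The point holds for the stepwise HRQoL models, on the condition that both arms are analysed and SHUTi has some effect outside insomnia. The bias then runs towards a false ISI effect, with a spurious slope of about 0.02 to 0.10 SD per SD over the assumed ranges. It is modest if SHUTi's ISI effect is near the detectable 0.31-0.45 SD and material if it is 0.8 SD or more. Effects of that order are not far-fetched, since Section 2.2 describes moderate to large CBTi effects on sleep. The rates rest on assumed effect sizes and on no within-arm correlation. The SEM, the analysis population and masking are unspecified; they are not shown to be wrong. The randomised comparison of ISI change, which is the primary analysis, is untouched. The change is worth making because the better model is specific and cheap.

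**What to change.** 1. State whether the models with ISI change as the causal variable use both arms or the SHUTi arm only, and correct the hypothesis label so that it agrees with Section 1.2.
2. If both arms are used, add randomised arm as a covariate to every such model: all four steps, and the ISI-change associations with distress, cardiac indices and HRQoL.
3. In the SEM, specify arm as an exogenous variable with direct paths to each mediator and to HRQoL, as well as through ISI.
4. Describe the ISI-change results as associational. A sensitivity analysis for unmeasured confounding would show how far within-arm confounding or shared reporting could explain them.

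The cost is SAP wording and one covariate that is known for everyone. If SHUTi moves ISI by 0.8 SD, arm explains 0.16/1.16 = 13.8% of the variance of ISI change, so the slope's standard error rises by a factor of 1/√(1 − 0.138) = 1.077, about 8%.
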